9.1.5. Electrocardiogram

Electrocardiograms (ECG) (12-lead) will be collected in triplicate within 5 minutes as per [Table 1](#), [Table 2](#), [Table 3](#), and [Table 4](#).

ECGs will be recorded after a participant has rested at least 5 minutes in the supine position. The following ECG parameters will be recorded: HR, PR, QRS, QT, and QTcF intervals.

ECG assessment will include interpretation of the tracings (eg, rhythm, presence of arrhythmia or conduction defects, any evidence of myocardial ischemia/infarction, or ST segment, T-wave, and U-wave abnormalities). The Investigator or designee is responsible for reviewing and over-reading the ECG interpretation, for assessing whether the ECG machine interpretation findings

are accurate, appropriate, normal, or abnormal, and for providing corrected interpretations as appropriate. In addition, any abnormal ECGs will be assessed for clinical significance.

Additional ECGs may be obtained if clinically indicated and must be obtained if abnormal and clinically significant or thought to be an error (eg, lead placement error, movement artifact, etc.). Any additional relevant data obtained by the Investigator during the course of this study will be supplied to the Sponsor.

For any ECG that the Investigator considers clinically significant, the Investigator will:

- Repeat the ECG.
- Follow-up ECG(s) will be obtained if any significant abnormalities are detected after dose administration to document resolution and as clinically indicated.
- Record as an AE any ECG that is 1) confirmed by the Investigator as clinically significant, 2) requires a participant to be discontinued from the study, or 3) requires a participant to receive treatment.

9.1.6. Laboratory Assessments

9.1.6.1. Standard Clinical Laboratory Assessments

Clinical laboratories described in [Table 13](#) will be collected as outlined in [Table 1](#) and [Table 3](#), and [Table 4](#). A certified laboratory will be utilized to process and provide results for the clinical laboratory tests. The Baseline laboratory test results for clinical assessment for a particular test will be defined as the last measurement prior to the first dose of study drug.

During Screening, if a participant has an out-of-range value for a clinical laboratory parameter that the Investigator believes is not clinically significant or that the Investigator does not believe is correct (eg, laboratory or specimen processing error), but the Investigator wants to confirm with a repeat laboratory test, a single repeat is allowed to confirm the initial result.

All out of-range values will be assessed by the Investigator as clinically significant or not clinically significant. For any laboratory test value outside the reference range that the Investigator considers clinically significant during the on-study period (ie, following dose administration), the Investigator will repeat the test to verify the out-of-range value and clinical significance.

Additional safety laboratory tests may be conducted as needed by the Investigator to evaluate participant safety.

9.1.6.2. Other Laboratory Assessments

Assessments of p50 and p20 will be conducted by hemoxygometry as indicated in [Table 1](#), [Table 3](#), and [Table 4](#). Assessments of RBC deformability and dense cells will be conducted as indicated in [Table 1](#), [Table 3](#), and [Table 4](#).

Assessments of serum erythropoietin (EPO) will be conducted as indicated in [Table 1](#) and [Table 3](#), and [Table 4](#).

Table 13: Clinical Laboratory Tests

Hematology	Coagulation	Chemistry	Urinalysis	Other
Hematocrit	International normalized ratio	ALT	Bilirubin	EPO
Hb		Albumin	Blood	FSH (post-menopausal females only)
RBC count	Prothrombin time	Alkaline phosphatase	Glucose	
Mean corpuscular volume	aPTT	AST	Ketones	Pregnancy - serum and urine (females only) ^b
Mean corpuscular Hb		Bicarbonate	Leukocytes	
Mean corpuscular Hb concentration		Blood urea nitrogen	Microscopic analysis of sediment if clinically indicated	Lipid Panel
Reticulocyte count (absolute and %)		Calcium	Nitrite	Amylase
Platelet count (estimate not acceptable)		Chloride	pH	Lipase
White blood cell count including differential count (percent and absolute):		Creatine phosphokinase	Protein	Hemoximetry
• Neutrophils		Creatinine	Specific gravity	RBC deformability and dense cells
• Lymphocytes		Fasting glucose	Urobilinogen	
• Monocytes		Lactate dehydrogenase		Serology Panel:
• Basophils		Magnesium		HIV 1/2 antibody
• Eosinophils		Phosphorous		Hepatitis A virus IgM antibody
		Potassium		Hepatitis B virus surface antigen
		Sodium		Hepatitis C virus antibody
		Total bilirubin (direct and indirect)		SARS CoV-2
		Total protein		
		Uric acid		
		eGFR ^a		
			Urine Drug screen	
			Cannabinoids	
			Amphetamines	
			Methamphetamines	
			Opiates	
			Methadone	
			Cocaine	
			Benzodiazepines	
			Phencyclidine, if clinical suspicion	
			Barbiturates	
			Alcohol breath test	

Abbreviations: ALT, alanine aminotransferase; aPTT, activated partial thromboplastin time; AST, aspartate aminotransferase; eGFR, estimated glomerular filtration rate; EPO, erythropoietin; FSH, follicle stimulating hormone; Hb, hemoglobin; HIV, human immunodeficiency virus; IgM, immunoglobulin M; PCR, polymerase chain reaction, RBC, red blood cells.

Note: Not all of these clinical laboratory tests are performed for safety purposes.

^a Using the using the Cockcroft-Gault formula.

^b Tests will be conducted at the clinic.

CCI

CCI

10. ASSESSMENT OF SAFETY — ADVERSE EVENTS

10.1. Adverse and Serious Adverse Events

10.1.1. Definition of Adverse Events

An AE is defined as any untoward medical occurrence associated with the use of a drug in humans, whether or not considered related to the study drug. An AE can therefore be any unfavorable and unintended sign, symptom, or disease temporally associated with the use of a study drug. An AE may also constitute complications occurring as a result of protocol-mandated interventions (eg, invasive procedures such as biopsies), including the period prior to receiving the first dose of the study drug (eg, medication washout). In addition to new events, any increase in the severity or frequency of a pre-existing condition occurring after the participant signs the ICF is considered to be an AE. This includes any side effect, injury, toxicity, or sensitivity reaction.

A suspected adverse reaction is any AE for which there is a reasonable possibility that the drug caused the AE. For the purposes of expedited safety reporting, “reasonable possibility” means there is evidence to suggest a causal relationship between the drug and the AE. Suspected adverse reaction implies a lesser degree of certainty about causality than adverse reaction, which means any AE caused by a drug.

A life-threatening AE or life-threatening suspected adverse reaction is an AE or suspected adverse reaction that, in the view of either the Investigator or Sponsor, places the study participant at immediate risk of death. It does not include an AE or suspected adverse reaction that, had it occurred in a more severe form, might have caused death.

An AE or suspected adverse reaction is considered to be “unexpected” if it is not listed in the Reference Safety Information section of the current IB or is not listed at the specificity or severity that has been observed.

10.1.2. Serious Adverse Event

A SAE or serious suspected adverse reaction is an AE or suspected adverse reaction that, at any dose, in the view of either the Investigator or Sponsor, results in any of the following outcomes:

- Death;
- A life-threatening AE;
- Inpatient hospitalization or prolongation of existing hospitalization;
- Persistent or significant incapacity or disability (substantial disruption of the ability to conduct normal life functions);
- A congenital anomaly/birth defect; or
- Important medical events that may not result in death, be immediately life-threatening, or require hospitalization may be considered serious when, based upon medical judgment, they may jeopardize the study participant and may require medical or surgical intervention to prevent one of the outcomes listed in this definition.

Note: Hospitalization planned prior to study enrollment (eg, for elective surgeries) is not considered to be an SAE. Hospitalizations that occur for pre-existing conditions that are scheduled after study enrollment are considered SAEs.

10.2. Severity

Whenever possible, the severity of all AEs will be graded using the National Cancer Institute Common Terminology Criteria for Adverse Events (NCI CTCAE), Version 5.0.

For AEs not adequately addressed in the NCI CTCAE, Version 5.0, the following criteria should be used.

- Grade 1 – Mild: Asymptomatic or mild symptoms; clinical or diagnostic observations only; intervention not indicated.
- Grade 2 – Moderate: Minimal, local or noninvasive intervention indicated; limited age-appropriate instrumental activities of daily living (ADLs).
- Grade 3 – Severe: Medically significant but not immediately life-threatening; hospitalization or prolongation of hospitalization indicated; disabling; limiting self-care ADLs.
- Grade 4 – Life-threatening: Life-threatening consequences; urgent intervention indicated.
- Grade 5 – Fatal: Death.

To make sure that there is no confusion or misunderstanding between the terms “serious” and “severe”, which are not synonymous, the following note of clarification is provided. The term “severe” is often used to describe the intensity (severity) of a specific event (ie, mild, moderate, or severe); the event itself, however, may be of relatively minor medical significance (eg, severe headache). This is not the same as “serious”, which is based on the study participant/event outcome or action criteria associated with events that pose a threat to a participant’s life or functioning. Seriousness (not severity) serves as a guide for defining regulatory reporting obligations.

10.3. Relationship to Study Drug

The relationship of an AE to the study drug should be determined by the Investigator according to the following definitions:

- **Not Related:** Evidence exists that the AE has an etiology other than the study drug and/or the temporal relationship of the AE/SAE to the study drug administration makes the relationship unlikely. If an SAE is not considered to be related to study drug, then an alternative explanation should be provided.
- **Related:** A temporal relationship exists between the event onset and the administration of the study drug and makes a causal relationship possible or probable. It cannot be readily explained by the participant’s clinical state or concomitant therapies and may appear, with some degree of certainty, to be related based on the known therapeutic and pharmacologic actions of the drug. Good clinical judgment should be used for determining causal assessment.

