3.4.2.3. Rationale for Evaluation of Higher Dose of GBT021601

As of Protocol Amendment 5, after a total of 8 weeks of treatment, all participants in this study demonstrated improvements in hematologic parameters, including reticulocytes and absolute reticulocytes, lactate dehydrogenase, and indirect bilirubin (Brown, 2021). Preliminary findings indicate a dose-related mean increase from about 15% to 32% in Hb occupancy after dosing with 50 mg daily and 100 mg daily respectively. Preliminary clinical safety data show that GBT021601 has been well tolerated with no significant treatment-related safety findings reported. An extended treatment period evaluating a dose escalation to 150 mg once daily for at least 6 weeks preceded by a loading dose of 300 mg, given twice daily over 4 days (the loading dose is being administered twice daily to minimize the potential for any gastrointestinal effect

that could theoretically occur with a higher once daily loading dose) is targeted to increase the Hb occupancy to approximately 54%. These projections were obtained from a population pharmacokinetic (PPK) model using the data from all 6 participants who have been enrolled in this study.

The Extended Treatment Period is being added to explore the safety and tolerability of these loading and maintenance dose levels. It is believed that higher Hb occupancy will translate to clinical benefits such as improved signs and symptoms of anemia, potentially reduced VOCs, and improved overall well-being in participants with SCD. To assess the full potential of this new agent, a formal multicenter dose-ranging study is being planned to evaluate higher doses of GBT021601, and it is critical to determine to safety/tolerability and effects on Hb occupancy and other hematological parameters at this proposed regimen (300 mg bid x 4 days plus 150 mg QD for 81 days).

CCI [REDACTED]

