10.4. Unexpected Adverse Reactions

An AE is “unexpected” if its nature and severity are not consistent with the information about the study drug provided in the Reference Safety Information in the IB.

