7.17.1 Adverse Events

All AE summaries will include treatment emergent AEs and will be presented for SCD related and SCD non-related separately.

SCD related AEs include:

SCD-related AEs comprise the following PTs: sickle cell anemia with crisis, ACS, pneumonia grouped terms (includes all PTs of pneumonia reported in this study), priapism, and osteonecrosis.

All AEs will be coded by primary system organ class (SOC) and preferred term (PT) according to the MedDRA Version 24.0 or higher and presented by participant in data listings.

The overall incidence of TEAEs (number of events, number and percentage of participants) will be summarized parts and overall. It includes: AEs, TEAEs, TEAEs by severity, SAEs, causally related TEAEs and SAEs, TEAEs leading to study or treatment discontinuation, life-threatening SAEs, and SAEs resulting in death.

The TEAEs will be summarized and tabulated at both the participant (n [%] of participants) and event (number of events) level:

- TEAEs by SOC and PT
- TEAEs by SOC, PT and maximum reported severity
- TEAEs by SOC, PT and closest relationship to study drug
- TEAEs by SOC, PT

For the incidence at the participant level by SOC and PT, if a participant experiences more than 1 event within the same SOC and PT, only 1 occurrence will be included in the incidence.

For the incidence at the participant level by SOC, PT, and severity, if a participant experiences more than 1 event within the same SOC and PT, only the most severe occurrence will be included in the incidence.

For the incidence at the participant level by SOC, PT, and relationship, if a participant experiences more than 1 event within the same SOC and PT, only the closest relationship will be included in the incidence.

Any SAEs, AEs with outcome of death, or AEs resulting in discontinuation of study or study drug will be listed separately.

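### The causality classes in Section 10.3 are stricter than Section 10.1.1 and leave a gap, so disease-like events may be under-counted as drug-related

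*Protocol*

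**What the plan says.** Protocol Section 10.3 gives the investigator two classes.

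- *Related* joins several conditions. The timing of the event relative to dosing "makes a causal relationship possible or probable". Then, of the event: "It cannot be readily explained by the participant’s clinical state or concomitant therapies". It should also appear related, with some certainty, in the light of the drug's known actions. The bullet ends with an appeal to clinical judgment.
- *Not Related* requires evidence that something other than the drug caused the event, or timing that makes a link unlikely, or both. An SAE placed here should come with an alternative explanation.

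Section 10.1.1 uses another standard: "A suspected adverse reaction is any AE for which there is a reasonable possibility that the drug caused the AE". For expedited reporting it explains this as having some evidence that points to a causal link. It sets no condition about the underlying disease.

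SAP Section 3.12.1 records relationship as one of two values, not related or related. SAP Section 7.17.1 counts causally related TEAEs and SAEs in its overall summary and tabulates "TEAEs by SOC, PT and closest relationship to study drug". It presents AE summaries separately for SCD-related and other events: "SCD-related AEs comprise the following PTs: sickle cell anemia with crisis, ACS, pneumonia grouped terms", with priapism and osteonecrosis completing the list.

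On expectedness, Section 10.1.1 calls an event unexpected if it is absent from the reference safety information or "is not listed at the specificity or severity that has been observed". Section 10.4 calls it unexpected if "its nature and severity are not consistent with the information about the study drug".

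**The concern.** Every participant has SCD, so many events on study will have a ready explanation in the participant's clinical state. The clause in 10.3 about that state is therefore not a rare exception here. It bears on exactly the events that the SAP sets apart as SCD-related.

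The trial is single-arm, with at least six participants and no formal tests, and its primary objective is safety and tolerability. Without a control group, all-causality counts cannot by themselves separate drug from disease, so the investigator's attribution is a main source of information on that question. If two sections set different thresholds, and the operative one leaves some events without a class, the related counts have no single meaning, and the text that speaks to the ambiguous events points away from *Related*.

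**Working it through.** No figure in the plan depends on this definition, so there is nothing to reproduce. The check is a comparison of the texts, followed by an illustration of scale.

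**1. Threshold and coverage.** Applying both sections to the same four kinds of event:

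| Event | Section 10.3 | Section 10.1.1 |
|---|---|---|
| Timing fits, no other ready explanation, fits the pharmacology | Related | Suspected reaction |
| Timing makes a link unlikely | Not Related | Not suspected |
| Timing fits, evidence that something else was the cause | Not Related | Generally not suspected |
| Timing fits, SCD is a ready explanation, no evidence that SCD was the cause | Neither | Suspected, if some evidence points to the drug |

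The fourth row is the defect. It fails *Related* because SCD readily explains the event. It fails *Not Related* because a possible explanation is not evidence of another cause. The data field still demands one of the two.

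One could close the gap by treating a ready explanation as evidence of another cause. The fourth row then becomes *Not Related*, and the conflict with 10.1.1 becomes direct. On either reading the sections need reconciling.

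**2. Which outputs use the label.** In SAP 7.17.1, the counts of causally related TEAEs and SAEs and the table by closest relationship use it. All TEAEs by system organ class and preferred term, TEAEs by severity, all SAEs and the SCD/non-SCD split do not. In the protocol, SAEs go to the sponsor whatever their attributed cause (10.6.1), and the criteria for an ad hoc SMC meeting include any AE of Grade 2 or above and any SAE (5.5.1).

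**3. Scale, on assumed inputs.** Let p be the chance that a participant has a truly drug-caused event, and q the share of such events that resemble SCD and are entered as not related. Neither is in the documents. With 6 participants, treated as independent:

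- expected participants with an event classed related = 6 × p × (1 − q)
- chance of at least one = 1 − (1 − p(1 − q))^6

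For p = 0.3 and q = 0.5: 6 × 0.3 × 0.5 = 0.90, and 1 − 0.85^6 = 0.623. Expected number, with the chance of at least one in brackets:

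| p | q = 0 | q = 0.5 | q = 1 |
|---|---|---|---|
| 0.1 | 0.60 (0.469) | 0.30 (0.265) | 0 (0) |
| 0.3 | 1.80 (0.882) | 0.90 (0.623) | 0 (0) |
| 0.5 | 3.00 (0.984) | 1.50 (0.822) | 0 (0) |

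The expected related count falls by the fraction q. All-causality counts do not change for any q. The last column is a limit in which every drug-caused event looks like SCD and none is called related; it is not a prediction.

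**4. Expectedness.** Section 10.1.1 joins specificity and severity with 'or'. Section 10.4 joins nature and severity with 'and', which can be read as needing both to differ. On that reading, a listed event at greater severity than listed is unexpected under 10.1.1 but not under 10.4. This is a minor mismatch.

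**The case against.** The best defence is that 10.3 is softer than its strictest clause. It accepts a merely possible link on timing, bars only what is readily explained, and leaves the decision to clinical judgment. Section 10.1.1 is also firmer than its headline phrase, since for expedited reporting it asks for some evidence of causation. The SAP shows disease-type events separately whatever their cause, and in a single-arm trial a looser rule would label some background crises as related too. All of this stands. It limits the consequence but does not make the two definitions agree or cover every event.

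Three stronger readings are tempting, and the documents do not support them.

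- *Disease-like toxicity can never be classed as related, so the related counts for SCD terms are zero by rule.* The softer wording above leaves room to class such events as related, and an event in the gap is not automatically *Not Related*. How investigators fill the gap is unknown.
- *Reportable reactions will be missed.* Section 10.6.2 gives expedited reporting to the sponsor, who receives every SAE. Nothing says that the sponsor relies only on the investigator's label. An effect is possible but not shown.
- *The case for Part C rests on this filter.* Section 3.4.2.3 does describe the drug as "well tolerated with no significant treatment-related safety findings reported", but it calls the data preliminary, does not say how relatedness was judged, and also draws on hematologic results and pharmacokinetic modelling. Section 5.7 names tissue hypoxia as the mechanism-related concern but does not say that it would appear as sickle-type events. Erythropoietin and reticulocytes, which Section 3.1 links to hypoxia, are measured in all three parts regardless of attribution.

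**Conclusion.** The point holds as a defect of definition. Section 10.3 sets a stricter standard than 10.1.1, and its two classes do not cover every event that a two-value field must record. The consequence is a risk of under-counting disease-like events in the causality-based tables. Its direction follows from the wording, on the assumption that investigators apply the printed definitions and more often resolve ambiguous events away from *Related*. Its size cannot be established, because the documents give no value for the share of events affected. Safety oversight that does not use attribution is untouched. The mismatch between 10.4 and 10.1.1 is real but secondary.

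**What to change.** In Section 10.3:

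- define *Related* as a reasonable possibility that the drug caused or contributed to the event, with a cross-reference to 10.1.1;
- define *Not Related* as everything else, so that each event has exactly one class;
- state that SCD as a plausible explanation is a consideration and does not by itself exclude relatedness.

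In Section 10.4, write 'nature or severity' to match 10.1.1. Carry the same wording into the eCRF completion guidance.

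Section 3.3.2 says that the Part A dose has been given and Part B dosing is complete, so a change now would leave two standards in one study. The report should state which standard applied to Part A and Part B events, or those events should be re-reviewed under the new wording. It should also read the related counts next to all-causality TEAEs by SCD-related status.

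The cost is wording plus that note or re-review. The downside is that more events will be labelled related, some of them background disease, with possibly a few more expedited reports.
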